In the past decades, the scientific focus regarding calcaneus fractures was the choice of operative or non-operative treatment modality. Although the evidence is ambiguous [1], recent meta-analyses suggest that operative therapy is associated with a higher likelihood to resume pre-injury work, to reach a higher level of physical function and fewer problems when wearing shoes. However, non-operative therapy has significantly less complications and infections [2,3]. Typically, aftercare includes non- or partial weight bearing, but protocols are different and often not very specific. In fact, there are no studies published comparing different procedures or special supporting devices. Recently, a heel-unloading orthosis ('Settner shoe' [4]) was introduced in aftercare for calcaneus fractures, allowing walking by shifting the load to the middle- and forefoot. This orthosis does not only enable early mobilization of patients suffering one-sided fractures, but also permits going following two-sided fractures, avoiding the otherwise necessary wheel-chair mobilization. The 'Settner shoe' can be applied in non-operative therapy and following operations. Specifically in calcaneus fractures, early regain of physical activity has been highlighted as one of the key factors for quality of life and the ability to return to work [2,3]. Thus, we hypothesize that mobilization with the 'Settner shoe' results in higher physical activity within the first 3 months and secondly improves ability to return to work in calcaneus fracture patients aged 18-60 years. Further outcome criteria are the American Orthopaedic Foot and Ankle Society's (AOFAS) ankle-hindfoot assessment, a 3-dimensional gait analysis, and the EQ-5D-3L questionnaire. It is the first trial applying a standardized aftercare in patients suffering from calcaneus fractures aiming to improve the non-operative part of treatment. Furthermore, the trial clarifies, whether the economical effort for the equipment acquisition is scientifically justified.

Objectives

We hypothesize that mobilization with the 'Settner shoe' results in higher physical activity within the first 3 months after calcaneus fractures.

Research questions

Does the application of a heel-unloading orthosis ('Settner shoe') independent of operative or non-operative therapy of a calcaneus fracture improve:

- 1.) the physical activity (active minutes per day)?
- 2.) the quality of life (EQ-5D-3L)?
- 3.) the foot function (AOFAS)?

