- 4.) the time necessary for return to work in patients between 18 and 60 years?

Trial design

The study design is a parallel group, randomized controlled trial with open allocation including all patients with calcaneus fractures independent of kind of initial therapy.

Methods: Participants, interventions, and outcomes

Study setting

All patients treated for calcaneus fracture (DS920* 'Fraktur af hælben' according to the Danish SKS-browser) at the University Hospital Odense are prospectively screened for eligibility and included in the trial, if they fulfil the inclusion criteria as listed below. The follow-up period is 6 months.

Eligibility criteria

In Denmark, the treatment of calcaneus fractures is regarded as highly specialized, wherefore both decision-making and operations are done for the whole Region of Southern Denmark in the Department of Orthopaedics and Traumatology at the University Hospital Odense. Therefore, patients are screened by consultants of the local trauma section.

Inclusion criteria:

- Fracture of the calcaneus, which is classifiable according to the Sanders' classification (excludes avulsion fractures)
- Being able to understand Danish or English and answer the questionnaires
- Informed consent
- Age between 18 and 65 years

Exclusion criteria:

- Pathological fractures
- Immature skeletal system
- Other fractures with influence on weight-bearing
- A soft-tissue situation not allowing the equipment with a 'Settner shoe' within 3 weeks after treatment (either decision-making for non-operative therapy or open reduction and internal fixation)

Acquiring patient consent

The participants will be introduced to the study by the medical personnel in a room, where they will not be disturbed. It will be assured that patients are allowed (if they wish) to be introduced to the study accompanied by a family member or any other person(s) selected by the patient. Patients will be given an oral overview of the purpose of the study, a participant information document describing the study and potential risk together with a patient consent form, which the patients will sign if they decide to participate in the study. The patient can resign from participating in the study without giving a reason and without any consequences. Patients are included after the operation or after decision for non-operative therapy, but before discharge.

Interventions

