- the time between the fracture occurred and operation or decision making for non-operative therapy

[figure not shown]
Healing and treatment characteristics

- bone healing after 3 months: union or delayed healing
The decision is made based on conventional radiographs including the clinical description of complains.
- weight bearing after 3 months
Is it possible or not?
- hindfoot axis (varus/valgus-deformity, Böhler angle, subtalar osteoarthritis)
The decision is made based on conventional radiographs and a clinical evaluation.
- type of operation (approach, fixation method, graft)

Complications

- infection (I)
- deep venous thrombosis (DVT)
- nerve paresis/palsy/disturbed sensibility (N)
- subtalar posttraumatic osteoarthritis (PTOA)
- subtalar instability (SI)
- local mechanical irritation by plate/screws (LI)
- wound irritations (WI) as superficial healing problems or skin edge necrosis
- irritations associated to the use of the custom-made heel-unloading orthosis ('Settner shoe')

Participant timeline

The clinical and radiological controls correlate with the usual guidelines for treating calcaneus fractures at the Odense University Hospital.

Sample size and power analysis

The sample size calculation was based on a 33% difference in activity, correlating with a clinical relevant difference. Setting the power to 80% and the 2-sided confidence interval to 95% the calculation according to the method of Fleiss with continuity correction resulted in 25 patients per group.

Recruitment

All consultants of the trauma section of the Department of Orthopaedics and Traumatology at the University Hospital Odense are involved in the recruitment process of the study.

Methods: Assignment of interventions (for controlled trials)

Allocation

In the period between treatment (either decision-making for non-operative therapy or open reduction and internal fixation) and consolidation of the soft-tissue situation, the patients are randomized for the aftercare with or without the custom-made heel-unloading orthosis ('Settner shoe'). As soon as the soft-tissue situation allows the adjustment, the patients are referred to an orthopaedic shoemaker, who equips the patient accordingly. The randomization is done using the tool provided by OPEN.

Blinding (masking)

The allocation is not blinded, because it will be obvious to the patient, whether a special shoe is worn or not. Furthermore, the treating trauma surgeon needs to initiate the prescription.

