Methods: Data collection, management, and analysis

Management and collection

REDCap™ (Research Electronic Data Capture), a secure application for online surveys and databases, facilitates data management. The University Hospital Odense is an institutional partner of REDCap™, which was especially designed for biomedical research and fulfills all necessary safety features. This is supported by the OPEN initiative (Odense Patient data Explorative Network). REDCap™ used with the OPEN-platform supports also a randomization function, which is used for the study.

Statistical methods

Normally distributed numeric data sets are compared using the paired Student's t-test. Otherwise or in case of non-numeric data, nonparametric tests determine the significance of difference. For correlations, Spearman ρ is calculated. Incidences are compared using the chi square test. Otherwise or in case of non-numeric data, nonparametric tests as the Mann-Whitney U-test for two and the Kruskal-Wallis H-test for multiple variables determine the significance of difference. For correlations, Spearman ρ is calculated.

Methods: Monitoring

Data monitoring

When the study is accepted for OPEN, a data manager will automatically be assigned to the study. The data manager will support the data coherence. Furthermore, a yearly data monitoring will be done by a study nurse, who is assigned to the project.

Harms

Any adverse or severe adverse events will be registered during the trial. Expected are especially local mechanical irritations, which are listed in the chapter for registration of patient characteristics beside outcome criteria.

Ethics and dissemination

Ethics

The study needs to be approved by the ethical board of the Region of Southern Denmark (<https://komite.regionssyddanmark.dk/wm258128>).

Patient law/privacy

All data collected from patients are protected by the Act on Processing of Personal Data and Health Act according to Danish Data Protection Agency. The project will be reported to Datatilsynet (under "Regionens Paraply 2012-58-0018"). The database is established with OPEN, however, other possible related files are stored in a secure Sharepoint (<https://secure.regionssyddanmark.dk/projektrum/ProTibExPla/SitePages/Startside.aspx>).

Publication

Reporting will be conducted according to Consolidated Standards of Reporting Trials (CONSORT guidelines (<http://www.consort-statement.org/>) and published in a peer reviewed journal.

Appendices

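### Free improvement: pre-specify adjustment of the primary comparison for operative status, and stratify the randomisation by it if recruitment has not started

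*Combined protocol and SAP*

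**What the plan says.** The research questions ask whether the orthosis would, "independent of operative or non-operative therapy of a calcaneus fracture improve", activity, quality of life, foot function and time to return to work. Trial design accordingly admits patients whatever their initial therapy.

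Operative status is known before allocation. Under Acquiring patient consent: "Patients are included after the operation or after decision for non-operative therapy, but before discharge". The Allocation section places randomisation after the operation or the non-operative decision.

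The method of randomisation is given in two places. Allocation says "The randomization is done using the tool provided by OPEN". Management and collection says that REDCap on the OPEN platform "supports also a randomization function, which is used for the study". Neither mentions strata, blocks or ratio. Equal groups are implied by the 25 per group in the sample size section.

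Statistical methods lists a t-test, nonparametric tests, a chi-square test and Spearman correlation. None of them takes a covariate or a stratum, and none is assigned by name to the primary outcome. Operative status appears in the analysis only as an explorative contrast of operated with non-operated patients. The indication for operative or conservative therapy and the type of operation are among the recorded characteristics.

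**The concern.** The background associates operative therapy with a higher level of physical function, and the primary outcome is physical activity. The listed reasons for choosing each therapy also differ: fracture displacement and shape on one side, comorbidity and smoking on the other. Operative status is therefore a plausible predictor of active minutes at 3 months, for reasons unrelated to the shoe.

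Two costs follow if it is left out of the primary comparison. When the arms happen to differ in share operated, part of the operative effect is counted as shoe effect. And even when the arms are balanced, the variation between operated and non-operated patients stays in the error term and costs power. With 50 patients, neither can be assumed negligible.

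**Working it through.** **The plan's own figure.** The sample size section uses "the calculation according to the method of Fleiss with continuity correction" for a 33% difference, 80% power and two-sided 5%. The two proportions are not given. Assuming 67% versus 100%:

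- Uncorrected: n = [1.96·√(2·0.835·0.165) + 0.842·√(0.67·0.33)]² / 0.33² = 18.6, so 19.
- Corrected: (18.6/4)·[1 + √(1 + 4/(18.6·0.33))]² = 24.3, so 25 per group.

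The stated 25 is reproduced (0% versus 33% gives the same). For a two-sample t-test on a continuous outcome, 25 per arm has 80% power at a difference of 0.81 SD (noncentral t, 48 df). The checks below use that difference and treat the t-test as unpaired.

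**Assumed inputs.** The documents do not give the share operated, the SD of active minutes or the effect of operative status. Assumed: 15 to 35 of 50 operated, and an operative effect g of 0.3 to 1.0 SD within operative groups.

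**Chance of imbalance.** If K of 50 are operated, the number X in one arm of 25 is hypergeometric(50, K, 25), and the imbalance is |2X − K|/25. Twenty points or more means |2X − K| ≥ 5.

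- K = 25: X ≤ 10 or X ≥ 15, probability 25.8%.
- K = 24 or 26: 2X − K is even, so the difference must reach 6 (24 points), probability 15.6%.
- K = 16 or 34: 12.8%, the lowest value from 15 to 35.

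The range is 13-26%, and its saw-tooth comes from odd and even K. With a random number operated (30-70%), the probability is 16-20%.

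**Consequence of a 20-point imbalance, half operated.**

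- Shift of the estimate = 0.20·g.
- Total SD = √(1 + 0.25g²); standard error = √(2/25) × total SD.
- With z = shift/SE, conditional type I error = Φ(−1.96 + z) + Φ(−1.96 − z).
- Share of variance removed by adjustment: R² = 0.25g²/(1 + 0.25g²).
- Adjusted power: noncentral t, 47 df, noncentrality 0.81·√12.5/√(1 − R²).

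| g (SD) | Shift (SD) | Conditional type I error, formula | Same, simulated, all trials ≥20 points | R² | Adjusted power, formula | Adjusted power, simulated |
|---|---|---|---|---|---|---|
| 0.3 | 0.06 | 5.5% | 5.6% | 2% | 81% | 80% |
| 0.5 | 0.10 | 6.4% | 6.6% | 6% | 82% | 81% |
| 0.8 | 0.16 | 8.2% | 8.8% | 14% | 85% | 85% |
| 1.0 | 0.20 | 9.7% | 10.1% | 20% | 88% | 87% |

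Simulations used 60,000 runs per scenario with half operated on average. The adjusted analysis held about 5% error in the imbalanced trials. Over all randomisations, the unadjusted test also held about 5%.

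On the same scale, the detectable 0.81 total SD is 0.81·1.01 = 0.82 within-group SD at g = 0.3 and 0.81·1.12 = 0.91 at g = 1.0. The shift is therefore 0.06/0.82 = 7% to 0.20/0.91 = 22% of the effect the trial can detect with 80% power.

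**Stratifying without adjusting.** With operative status balanced by design but left out of the test, simulated type I error was 4.3%, 3.4% and 2.9% at g = 0.5, 0.8 and 1.0. The test becomes conservative, so the factor belongs in the model as well.

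**The case against.** Simple randomisation followed by an unadjusted test is a valid design, and chance imbalance is not systematic bias. That stands: the 5.5-10% applies only to the minority of trials with a large imbalance.

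The size of the operative effect on active minutes is unsupported by any figure. The background calls the evidence on operative treatment ambiguous, and within each arm the same aftercare schedule applies to both kinds of patient. At 0.3 SD the cost is negligible, with power rising by a point at most. An effect of 1.0 SD would exceed the difference the trial can detect for the shoe itself, so the upper end of the range is generous. This limits the size of the point, but adjustment costs almost nothing even at 0.3 SD.

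A reader might infer that the randomisation is known to be unstratified. The documents are silent: stratification is neither planned nor excluded, and the tool may be set up with it. A reader might also infer that operative status is ignored altogether. It is recorded and has its own explorative comparison, although that comparison does not adjust the shoe effect.

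The same argument could be made for bilateral fractures, which are eligible and which the background associates with wheelchair mobilisation. But the documents give no frequency, and laterality is not among the listed characteristics; it appears only in the tracker-placement rule.

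**Conclusion.** The point holds as a free improvement, not as an error that invalidates the analysis. A known, recorded and plausibly prognostic baseline factor is left out of the primary comparison, and no stratification by it is specified.

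The documents do not support the stronger readings that a material imbalance is likely or that the unadjusted test has an inflated error rate. The chance of 20 points or more is 13-26%, and overall type I error stays at about 5%. What is at stake is conditional error in an imbalanced trial (about 5.5-10%, with a shift of 0.06-0.20 SD) and forgone power (80% against about 81-88%). Both rest on the assumed share operated and the assumed operative effect of 0.3-1.0 SD; at the lower end the gain is close to nil.

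**What to change.** - Pre-specify the primary analysis of active minutes per day at 3 months as a linear model on arm plus operative status (operated or not), reporting the adjusted difference with its 95% confidence interval. Fix this before outcome data are examined; adjustment chosen after an imbalance is seen would be post hoc.
- State the randomisation scheme: ratio, strata and type of blocking.
- If recruitment has not started, stratify the REDCap/OPEN randomisation by operative versus non-operative therapy, with permuted blocks of varying size, and keep the factor in the model. If recruitment is under way, make the adjustment alone.
- Add laterality as a covariate only if it is first made a recorded data item.

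The cost is a paragraph in the analysis plan and, where still possible, a change to the randomisation set-up (the documents do not describe the tool's options, so this needs confirming with OPEN). Operative status is already recorded, and no additional patients, visits or measurements are needed.

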After operation or decision for non-operative therapy, the schedule for the 2 groups are defined as follows:

Group 1 (treatment without 'Settner shoe'):

- mobilization without weight bearing for 6 weeks starting with the day of either decision-making for non-operative therapy or open reduction and internal fixation, if needed a cast or another kind of orthosis as a Static Walker are applied, then 4 weeks 15-20 kg, 2 weeks 35-45 kg, after that transition to full-weight bearing (always only if possible)

- X-ray after 6 and 12 weeks; depending on the results, the schedule for weight bearing may be adjusted to the need in case of delayed healing or complications related to implants

Group 2 (treatment with 'Settner shoe'):

- mobilization with the custom-made heel-unloading orthosis ('Settner shoe') without pads for 6 weeks, then 2 weeks one pad, 2 weeks 2 pads, 2 weeks 3 pads, after that full-weight bearing without any support (always only if possible)
- X-ray after 6 and 12 weeks; depending on the results, the schedule for weight bearing may be adjusted to the need in case of delayed healing or complications related to implants

The patients of both groups are informed about the aftercare at the time point of inclusion.

Outcomes

Primary outcome criterion

The number of active minutes per day following 3 months (time point 2) is primary outcome criterion.

Secondary outcome criteria

- active minutes per day at time point 1
- portion of highly active periods per day at time point 1 and 2
- the EuroQol 5D-3L questionnaire following 3 months (time point 2)

Explorative outcome criteria

- AOFAS
- 3-dimensional gait analysis
- time point of return to work of patients between 18 and 60 years
- range of motion (ROM)
- Pro- and supination (percent of healthy side or assumed normal mobility) are analyzed.
- pain
- The evaluation includes the medication and a visual-analogue scale (VAS).
- comparison between patients with and without operation

Patient characteristics beside outcome criteria

Epidemiology

- age
- sex
- body mass index
- ASA (American Society of Anesthesiologists) physical status classification system

Injury characteristics

- classification according to Sanders (figure 4)
- classification of open/closed tissue damage (table 1)
- polytrauma (ISS \geq 16, multiple injuries, monitrauma)
- indication for operation (dislocation, broadening, flattening of Böhler angle etc.) or conservative therapy (comorbidity, smoking etc.)

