Measurement of physical activity

For monitoring of activity, the patients are equipped with a Misfit™ Shine (Burlingame, CA, USA) at the ankle and an Axivity™ AX3 (Newcastle upon Tyne, UK) at the lateral femur of the unaffected side. If there is a fracture at both sides, the trackers are attached to the side with the less complicated fracture. The wear time is 7 days. At day 7±14 (discharge) and after 3±0.5 months patients are equipped, and activity signals are analyzed by calculating the mean of all acquired 24-hour-data during these two periods. Regarding the Misfit™ Shine, only the number of registered steps is recorded. Regarding the Axivity™ AX3, the portion of highly active periods per day and the number of active minutes, correlating with walking activity, have shown to be most discriminating in the preliminary validation study. Therefore, these parameters are selected. Reliability is checked using a wear-time analysis based on change of signal vector magnitudes and temperature monitoring.

Correlating with these two data points, the EuroQol 5D-3L questionnaire [5] and the AOFAS [6] are monitored.

Classification

Classification of calcaneus fractures according to Sanders

[figure not shown]

Figure 3: Axial load is necessary for calcaneus fractures, which should be treated with a heel-unloading 'Settner shoe'.

[figure not shown]

Figure 4: The fracture classification according to Sanders can group the calcaneus fractures that occur following axial load [7].

Classification of open fractures according to Gustilo-Anderson

| Gustilo Grade | Definition |
|---------------|--|
| I | Open fracture, clean wound, wound <1 cm in length |
| II | Open fracture, wound > 1 cm but < 10 cm in length without extensive soft-tissue damage, flaps, avulsions |
| III | Open fracture with extensive soft-tissue laceration (>10 cm), damage, or loss or an open segmental fracture. This type also includes open fractures caused by farm injuries, fractures requiring vascular repair, or fractures that have been open for 8 hr prior to treatment |
| IIIA | Type III fracture with adequate periosteal coverage of the fracture bone despite the extensive soft-tissue laceration or damage |
| IIIB | Type III fracture with extensive soft-tissue loss and periosteal stripping and bone damage. Usually associated with massive contamination. Will often need further soft-tissue coverage procedure (i.e. free or rotational flap) |

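### For normally distributed outcomes the plan names only a paired t-test, although the randomised arms contain different patients and no pairing is defined

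*Combined protocol and SAP*

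**What the plan says.** Under Statistical methods, the rule for normal numeric data is: "Normally distributed numeric data sets are compared using the paired Student's t-test". It is the only parametric test of difference in the document, and it is not restricted to repeated measurements on the same patient. For data that are not normal or not numeric, the section names "nonparametric tests as the Mann-Whitney U-test for two and the Kruskal-Wallis H-test for multiple variables".

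The design is stated under Trial design: "The study design is a parallel group, randomized controlled trial with open allocation". Under Allocation, "the patients are randomized for the aftercare with or without the custom-made heel-unloading orthosis", and "The randomization is done using the tool provided by OPEN". No matching, pair randomisation or crossover is described.

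The primary outcome is a single numeric value per patient: "The number of active minutes per day following 3 months (time point 2) is primary outcome criterion". The appendix on measurement of physical activity gives two wear periods: "At day 7±14 (discharge) and after 3±0.5 months patients are equipped".

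**The concern.** A paired t-test needs a defined partner for each observation. Here the two arms hold different people, and nothing links a patient with the shoe to a particular patient without it. Read literally, the rule can be applied in two ways, and neither works for the primary question.

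- **Pairing across arms.** Unrelated patients are lined up in some order, for example database row order. The standard error then depends on that order, and the test cannot use everyone if the arms differ in size.
- **Pairing within patients.** The two wear periods are natural pairs, but comparing them tests recovery over time and not the effect of the shoe. The between-arm comparison of normal data would then have no named test.

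At stake is whether the plan fixes one answer to its primary question. Allocation is open, and the choice of row order would lie with whoever runs the analysis. An analyst who sensibly uses an unpaired test instead would be departing from the written plan on the primary endpoint.

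**Working it through.** **Inputs.** From the document: 25 patients per group, 80% power, two-sided 5%, a 33% difference in activity, and the Fleiss method with continuity correction (Sample size and power analysis). The document gives no standard deviation, baseline rate or dropout rate. Assumed: normal data with SD 1.

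**1. The plan's own figure.** The Fleiss formula compares two independent proportions. With p1 = 1.00, p2 = 0.67, difference 0.33 and mean proportion 0.835:

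- n' = [1.96·√(2·0.835·0.165) + 0.842·√(0 + 0.67·0.33)]² / 0.33² ≈ 18.6
- n = (n'/4)·[1 + √(1 + 4/(n'·0.33))]² ≈ 24.3, rounded up to **25 per group**

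So 25 is reproduced at these boundary rates (equivalently 0% v 33%). Other baselines with a 33-point difference need up to 41. Whether a formula for proportions suits a numeric outcome is a separate matter. What counts here is that the sample size was planned for independent groups.

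**2. Why row order matters.** With n per arm and arm SDs s1 and s2:

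- Unpaired: t = (mean1 − mean2) / √[(s1² + s2²)/n]
- Paired: t = (mean1 − mean2) / √[(s1² + s2² − 2·r·s1·s2)/n]

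Here r is the sample correlation produced by the chosen line-up. With equal arms the mean difference is the same under every order; only the standard error, interval and p-value move. If s1 = s2, paired t = unpaired t / √(1 − r).

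Under random ordering of 25 rows, r has mean 0 and SD 1/√24 = 0.204, so about 95% of orders give r between −0.40 and +0.40. Take an unpaired p of 0.03 (t = 2.24 on 48 df):

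- r = +0.40: t = 2.24/√0.60 = 2.89, p ≈ 0.008 on 24 df
- r = −0.40: t = 2.24/√1.40 = 1.89, p ≈ 0.071 on 24 df

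The critical value also rises, from 2.011 (48 df) to 2.064 (24 df).

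**3. Simulated row orders** (20,000 trials, 1,000 random orders each):

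| Welch p | Median central 95% range of paired p | Orders with p < 0.05 |
|---|---|---|
| 0.009–0.011 | 0.002–0.032 | over 99.9% |
| 0.028–0.032 | 0.009–0.069 | 80.7% |
| 0.045–0.055 | 0.017–0.100 | 41% |

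The approximation in step 2 agrees with the middle row. Each verdict is reached by at least 5% of orders in 18.8% of trials at d = 0.809, and in 7.8% under no effect.

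**4. Operating characteristics** (200,000 trials per scenario). The effect d = 0.809 is the one that an unpaired t-test detects with 80% power at 25 per arm. It is not the plan's 33% difference, which cannot be standardised without an SD. When arms are unequal, surplus patients are dropped to form pairs.

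| Arms | Effect | Welch rejects | Paired rejects | Verdicts differ |
|---|---|---|---|---|
| 25 v 25 | none | 4.9% | 5.0% | 1.8% |
| 25 v 25 | 0.809 | 80.0% | 78.4% | 4.9% |
| 25 v 24 | 0.809 | 79.0% | 76.5% | 6.3% |
| 25 v 22 | 0.809 | 77.1% | 72.4% | 9.4% |
| 25 v 20 | 0.809 | 74.9% | 67.9% | 12.2% |

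Paired type I error is 5.0% throughout. The unequal sizes are assumptions. No figure can be given for the within-patient reading, because the document states neither the size of recovery nor the correlation between wear periods.

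**The case against.** The strongest reply is that the sentence may not govern the primary comparison. The section falls into two blocks, each with its own fallback to nonparametric tests. The first holds the paired t-test. The second holds the chi-square, Mann-Whitney and Kruskal-Wallis tests, all for independent groups. The first block could be meant for within-patient comparisons, which would leave Mann-Whitney as the primary test. More simply, the word may be a slip, since the other group tests and the sample size method all assume independent groups.

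Either may be what was meant, but the text says neither. On the first reading the plan still has no parametric test between arms. On the second, the error stands uncorrected in the only analysis text there is.

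Some limits on the harm do stand:

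- With equal arms the estimated difference does not change with row order.
- Any order fixed in advance gives a repeatable p-value and a valid 5% test. The fault is that no order is specified, so one could be chosen.
- Only borderline results are sensitive. By the 5%-of-orders criterion, about 81% of trials at d = 0.809 are not.
- The larger power losses rest on assumed unequal arms.

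**Conclusion.** The concern holds. For normally distributed outcomes, including the primary one if it is judged normal, the stated test does not fit the design, and its p-value and confidence interval are undefined until a pairing is invented.

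The numerical harm with equal arms is small: no inflation of type I error and a power loss of 1.6 points (80.0 − 78.4). The reason to correct it is that a near-threshold primary result could be declared significant or not from the same 50 values. With unequal arms, randomised patients are also discarded and the estimate itself depends on who is dropped.

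These sizes assume normal data with equal SDs, random line-up and, for the unequal arms, losses that the document does not state. That the test is mis-specified needs none of these assumptions. The Mann-Whitney branch is unaffected.

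**What to change.** Before any data are analysed, replace the sentence in Statistical methods with wording such as:

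> Normally distributed numeric outcomes are compared between the randomised groups, and between other groups of different patients, with an independent-samples (unpaired, Welch) t-test, reported as a mean difference with 95% confidence interval. Paired tests are used only for comparisons within the same patient.

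The essential change is from paired to unpaired. The Welch form and the reported interval are sensible additions but are not needed to cure the error. The Mann-Whitney and Kruskal-Wallis rules can stay. Whether to keep choosing the test by a check of normality is a separate question.

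The cost is one sentence. It needs no new data and does not alter the 25 per group, which already comes from a formula for independent groups.
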